Participants will complete a telephone screening, an in-person baseline, and an online webinar (described above). Eligible participants will then be randomized to one of two 12-month weight loss interventions: online (Get Social) or in-person (Traditional). Follow-up assessments will occur at 6- and 12-months.

Randomization: Randomization will take place after the baseline procedures are complete once we've determined eligibility. Participants will be randomized to the Get Social or the Traditional condition. We will randomize 36-40 participants for each recruitment wave, for a goal of approximately 18 per condition. Participants will be randomized 1:1 to the two study conditions in randomly permuted blocks of size 4 and 6 using the ralloc program in Stata Randomization and will be stratified by gender (male vs. female) and baseline BMI (27.0-34.9 vs. 35.0-45.0). The randomization list was generated at the start of the study before randomization. The list is managed by the program director. Once a participant has been determined to be eligible, the program director will assign each participant to the next open assignment on the list. The program director will then tell the research assistant who will reach out to participants to inform them via e-mail of the condition assignment.

Orientation-Visits:

- Traditional participants: This in-person group will last 1 hour and will include training on The first session of the intervention will be extended from 1.5 hours to 2 hours in order to provide time for the orientation which will cover: -My Fitness Pal, an overview of their participation, and study goals. My Fitness Pal is an app that can be used to track diet and physical activity. It can be used on a computer or mobile app. Participants will receive their study goals for weight loss (1-2 lbs. per week), diet, and physical activity. The weight loss goal is approximately 7% weight loss over a 12 month period. This orientation may be completed on an individual in-person basis or phone for people unable to attend the group, though this option won't be encouraged. The weight loss goal is provided in the My Fitness Pal app. –The orientation group is led by the interventionist, a post-doctoral fellow, and a research assistant. and research assistants.

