- Traditional participants will receive the DPP intervention during in-person group visits. Groups will include 18 participants each. During the first 6 months, groups will be held weekly for 8 weeks, then biweekly for 16 weeks. Groups will be held monthly between 6- and 12-months. There will be a total of 22 groups and each group will last 90 minutes (except for the first group which will be extended to 2 hours to accommodate the orientation) and each one will be audio recorded to track intervention-adherence. Participants will have weight taken in-person before the start of each group. During the weeks participants do not have a group, they will be encouraged to take their weight at home and e-mail it to study staff. Staff will e-mail them during these weeks asking for their current weight. The e-mail text wording is included in the measures attachment.
- Get Social participants will receive the DPP intervention in a "protected" Twitter group. Where participants and counselors will activate the "protected tweets" privacy setting so that the tweets are only viewable to each other. The DPP content has been restructured to deliver in an online context. The delivery includes a morning and evening post each day. The online coaches will log in twice daily to respond to questions, address concerns, and encourage engagement. Participants will receive an e-mail asking for their current weight, the minutes per week they used Twitter, and questions about treatment receipt. These e-mails will be sent during the same weeks that the Traditional participants have a group. The questions for this survey will all appear together accessible by one link. See measures attachment for survey. When reporting time on Twitter, participants will Androids will be asked to download an app called App Usage Tracker. This app is free and downloaded from the Play Store and tracks time spent on apps.
- Interventionists will be asked at to complete a survey at the 6 month timepoint. The survey link will be emailed at the 6 month time point in each wave. The survey will ask about their experience delivering the intervention. If they do not respond we will follow up with them via email or phone. Once they have delivered interventions to participants in both the Get Social and Traditional conditions the survey will also ask for their opinions comparing and contrasting their preferences for each condition.

Follow up:

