Chronic Pain	Brief Pain Inventory ¹⁸	Х		X	Х	REDCap
Quality of Life	EQ-5D-3L ¹⁹	X		X	Х	REDCap
Contamination	Weight-loss related social media use*	X			X	REDCap
Social media use	Social Media Use*	Х		Х	Х	REDCap
Dietary recall	3 24hr recalls (ASA24- Automated Self- Administered) ²⁰	X (3)		X (3)	X (3)	Online
Social support for weight management	WMSI ²¹	X		X	X	REDCap
Measure time spent on Twitter	Phone or app tracking		X			REDCap
Group engagement on Twitter	Engagement in group		X	X	X	Twitter
Treatment receipt	Questions each week related to intervention*		X			REDCap
Intervention acceptability and burden	Questions given at 6m follow-up* and time spent data extraction from getsocial.com			X	X	REDCap
Interventionist Feedback (Interventionists only)	Interventionist Survey*			X		REDCap

* Investigator-derived items

Data Analysis: [For all studies, specify the analytic techniques the researcher will use to answer the study questions. Indicate the statistical procedures (e.g. specific descriptive or inferential tests) that will be used and why the procedures are appropriate. For qualitative data, specify the proposed analytic approaches.]

Preliminary analysis

Baseline participant characteristics will be examined by condition. If groups differ on certain characteristics, these variables will be included as covariates in the primary analyses. Other preliminary analyses include assessing patterns of missing data, dropout rates, distributional properties of dependent measures, and correlations among outcome measures. A series of sensitivity analyses will be performed to examine the extent of potential bias by assuming the participants who dropped out are (i) missing completely at random (i.e., independent of the outcome), (ii) are responders to the intervention, or (iii) are non-responders to the intervention. Multiple imputation to impute missing data will be used if more than 5% of data are missing.

Primary non-inferiority outcome

We will model percent weight loss at 12 months using a linear regression model framework, with percent weight loss as the dependent variable and study condition as the independent variable. Test of the intervention condition indicator will provide a statistical test of the intervention effect and the estimated coefficient, along with the

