2/26/2021

Statistical Analysis Plan

Study Title: Get Social: Randomized Trial of a Social Network Delivered Lifestyle Intervention

NCT02646618

Preliminary analysis

Baseline participant characteristics will be examined by condition. If groups differ on certain characteristics, these variables will be included as covariates in the primary analyses. Other preliminary analyses include assessing patterns of missing data, dropout rates, distributional properties of dependent measures, and correlations among outcome measures. A series of sensitivity analyses will be performed to examine the extent of potential bias by assuming the participants who dropped out are (i) missing completely at random (i.e., independent of the outcome), (ii) are responders to the intervention, or (iii) are non-responders to the intervention. Multiple imputation and other methods will be explore to address missing data for variables for which more than 5% of data are missing.

Primary non-inferiority outcome

We will model percent weight loss at 12 months using a linear mixed model, with percent weight loss as the dependent variable and study condition as the independent variable and accounting for repeated measures of weight. Test of the intervention condition indicator will provide a statistical test of the intervention effect and the estimated coefficient, along with the estimated confidence interval. This analytic approach aims to test whether the Get Social condition is not appreciably worse than (i.e., not inferior to) the traditional condition for percent weight loss at 12 months by our a priori inferiority margin of 2%. The effect estimates will reveal clinical non-inferiority of the Get Social condition if the confidence interval lies completely above $-\Delta$ or clinical non-inferiority of the traditional condition if the confidence interval lies completely below $+\Delta$, i.e., 2%.

Secondary non-inferiority outcomes

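### No specified dropout check shows how far missing Get Social participants must fall short before non-inferiority fails; MVPA separately rests on baseline carried forward

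*SAP*

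**What the plan says.** The SAP (Preliminary analysis) plans three sensitivity scenarios for dropout. The Protocol (Data Analysis, Preliminary analysis) has the same list, which opens by "assuming the participants who dropped out are (i) missing completely at random". The other two scenarios are that dropouts "ii) are responders to the intervention, or (iii) are non-responders to the intervention". Neither document turns responder or non-responder into a percent weight loss, or says whether the two arms are treated alike.

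The SAP adds: "Other preliminary analyses include assessing patterns of missing data, dropout rates". It also says: "Multiple imputation and other methods will be explore to address missing data for variables for which more than 5% of data are missing". The Protocol is firmer and commits to multiple imputation above the 5% threshold. Neither document describes an imputation model or any departure from missing at random (MAR).

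The SAP's primary analysis is a linear mixed model for 12-month percent weight loss, "accounting for repeated measures of weight". Get Social is non-inferior if the confidence interval lies wholly above -2%; no confidence level is given. The Protocol (Justification of Sample Size) assumes SD 5.5%, 131 evaluable per arm and 20% attrition.

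For MVPA, the SAP (Secondary non-inferiority outcomes) models the proportion reaching 150 minutes per week by GEE. A missing follow-up status is replaced by the baseline status.

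**The concern.** In a non-inferiority trial the damaging departure is one-sided: missing participants in the new arm do worse than the model assumes. The listed scenarios do not measure it.

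- Missing completely at random is stronger than the MAR assumption behind the mixed model, so it cannot stress that model. Multiple imputation under MAR does not stress it either.
- The responder and non-responder scenarios are undefined for a continuous outcome. If each is read as one common value in both arms, which is one possible reading, equal dropout pulls the arms together. That favours non-inferiority when Get Social is doing worse.

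If non-inferiority is concluded, a reader could not tell from the specified checks whether it would survive a plausible shortfall among missing Get Social participants. Values chosen after the results are seen could settle a borderline robustness claim.

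For MVPA, carry-forward treats imputed values as observed, so part of the reported contrast reflects the rule and the split of missingness between arms.

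**Working it through.** **Inputs.** From the Protocol (Justification of Sample Size): margin 2, SD 5.5, true difference 0, power 90%, 131 evaluable and 164 enrolled per arm, 20% attrition.

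**The plan's own figure.** n per arm = 2 × (1.645 + 1.282)² × 5.5² / 2² = 130 by the normal formula. The noncentral t gives 131, with power 90.2%. Then 131 / 0.8 = 164. One-sided 0.025 would need 159 (t: 160), and power at 131 would be 83.5%. The design therefore rests on one-sided 0.05, that is, a 90% two-sided interval. The 95% results are also shown because the SAP states no level.

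**Tipping point.** SE = 5.5 × √(2/131) = 0.680. If a fraction d of Get Social is missing and those participants lose delta points less than their MAR values, the estimate falls by d × delta. The limit reaches -2 at delta = (estimate - z × SE + 2) / d. With d = 0.2:

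- Estimate 0, 90%: (0 - 1.118 + 2) / 0.2 = 4.41. At 95%: (0 - 1.332 + 2) / 0.2 = 3.34.
- Estimate -0.5, 90%: (-0.5 - 1.118 + 2) / 0.2 = 1.91. At 95%: (-0.5 - 1.332 + 2) / 0.2 = 0.84.

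Other missing fractions at estimate 0 (90% / 95%):

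- 10% missing (147.6 per arm, SE 0.640): 9.47 / 7.45.
- 30% missing (114.8 per arm, SE 0.726): 2.69 / 1.92.

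Adding the variance of the shift, d(1 - d) × delta² / 164, lowers the 20% values at estimate 0 only to 4.30 / 3.27.

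**Common-value reading.** With equal dropout d and one value c in both arms, the c terms cancel and the difference becomes (1 - d) times the completer difference. Assume completer means of 7% (Traditional) and 6% (Get Social), with d = 0.2.

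- Completers: difference -1.0; 90% lower limit -1.0 - 1.645 × 0.680 = -2.12 (fails); 95% limit -2.33.
- All dropouts set to 0%: difference 4.8 - 5.6 = -0.8. Arm variances are 0.8 × 30.25 + 0.16 × 36 = 29.96 and 0.8 × 30.25 + 0.16 × 49 = 32.04. SE = √((29.96 + 32.04) / 164) = 0.615. The 90% limit is -1.81 (passes). The 95% limit is -2.005 (still just fails).
- All dropouts set to 7%: difference -0.8, SE 0.544, 90% limit -1.70 (passes).

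So under this reading a scenario labelled non-responder can turn a 90% failure into a pass. With unequal dropout the difference can move either way.

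**MVPA.** Assume follow-up rates among those observed of 40% (Get Social) and 50% (Traditional), and a 20% baseline rate among those missing in both arms.

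- 20% missing in each arm: 0.8 × 40 + 0.2 × 20 = 36 against 0.8 × 50 + 0.2 × 20 = 44. The 10-point gap becomes 8, whatever the common baseline rate.
- 25% missing in Get Social, 15% in Traditional: 35 against 45.5, a gap of 10.5 (11.5 to 8.5 for baseline rates of 10 to 40%).
- 15% missing in Get Social, 25% in Traditional: 37 against 42.5, a gap of 5.5 (4.5 to 7.5).

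**The case against.** The plan is not silent on missing data. It examines dropout and missing-data patterns, uses earlier weights in the mixed model and provides for multiple imputation, firmly so in the Protocol. The undefined terms leave room for arm-specific values. At the design assumption of no difference, missing Get Social participants alone would have to fall 4.4 points short, which is not small. All of this stands. It does not supply the missing check, because the mixed model and MAR imputation share one assumption, and permission to choose values later is not prespecification.

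Four stronger readings are tempting but unsupported:

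- A reader might infer that the plan fills both arms with one value and so leans toward non-inferiority. The documents do not say this. Filling each arm from its own responders or non-responders is equally open.
- A reader might infer an inflated type I error. The scenarios are sensitivity analyses, not the decision rule.
- A reader might want a sharp mean loss above which setting only Get Social dropouts to 0% fails. That threshold depends on the variance method: at estimate 0 it is about 4.4 to 4.8% (90%) or 3.3 to 3.9% (95%). It also supposes one-sided failure that nothing in the documents predicts.
- A reader might infer that the weight history is collected differently by arm. For Traditional the Protocol says "Participants will have weight taken in-person before the start of each group", and for Get Social "Participants will receive an e-mail asking for their current weight". But Traditional participants are also asked by e-mail for home weights in weeks without a group, and the SAP does not say that between-visit weights enter the model.

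On MVPA, the rule is fully prespecified. That is a merit, but it does not make imputed values observed.

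**Conclusion.** The point holds as a gap in the specified sensitivity analyses, not as a flaw in the primary decision rule. At the plan's figures with 20% missing, non-inferiority fails once missing Get Social participants lose about 4.4 points (90% interval) or 3.3 points (95%) less than their MAR values at an estimate of 0, and 1.9 or 0.8 points less at -0.5. An unfavourable estimate within the margin is therefore fragile, and nothing specified would show it. These figures assume the planned SD, 131 evaluable per arm and no precision gained from repeated weights. The -2.12 to -1.81 example assumes the common-value reading, equal dropout and the stated completer means.

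For MVPA, carry-forward pulls the arms together when baseline rates and missingness are balanced; otherwise the direction varies. The rates used are assumptions. No margin is stated for the 150-minute proportion, so no effect on a verdict is claimed.

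**What to change.** - Keep the mixed model as primary.
- Add a delta-adjusted tipping-point analysis. Impute missing 12-month weights under MAR by arm, using the staff-measured baseline and 6-month assessment weights, which are collected the same way in both arms (Protocol, Study Design: "Follow-up assessments will occur at 6- and 12-months"). Penalise missing Get Social values only, and increase delta until the lower limit crosses -2%. Report that delta with dropout by arm.
- If the responder and non-responder scenarios are kept, state the percent weight loss assigned. Apply it only where the 12-month weight is missing, because the Protocol lets participants leave the intervention and still complete the final assessment.
- For MVPA, run the GEE on multiply imputed data and report baseline carried forward as a sensitivity analysis.

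The cost is SAP wording and modest programming, with no new data. A borderline non-inferiority result may be shown to be fragile, and the MVPA interval may be wider.

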Participants will complete follow-up visits at 6- and 12-months. The visit will last 1 hour and will include a weight measurement, blood pressure reading, three 24-hour diet recall interviews, and repeated baseline measures. The online survey containing the measures will be e-mailed to participants 1 week prior to the scheduled follow-up visits.

Time Commitment:

Visit	GS Condition	TC Condition
	(in minutes)	(in minutes)
Telephone Screening (20 min)	20	20
Baseline (210 min total)	210	210
Visit (90 min)		
2 at-home dietary recalls (60 min)		
Online survey (60 min)		
Webinar (60 min)	60	60
Orientations	180	

GS: individual orientation (60 min)		
GS: group orientation (120 min)		
TC: group orientation (60 min)		
Intervention	750	1980
GS: approx. 35 min/week 8 weeks, 14 min/week		
for 16 weeks, 8 min/week for 28 weeks (12.5 hrs)		
TC: 22 1.5 hr groups (33 hrs)		
6-month (150 min total)	150	150
Visit (30 min)		
2 at-home dietary recalls (60 min)		
Online survey (60 min)		
12-month (150 min total)	150	150
Visit (30 min)		
2 at-home dietary recalls (60 min)		
Online survey (60 min)		
Total	1520 minutes	2630
	(approx. 25 hrs)	2570 minutes
		(approx. 434
		hrs)

Interventionist data collection:

The interventionists provide the following information, some of which will be used in the analysis:

- Weekly timesheets for invoicing their time (these hours are used to calculate time/cost needed to deliver the intervention aim 2).
- A 10 minute survey at the end of each 6-month phase for each wave used to gather interventionist feedback.

Measures

Data Collected	List of Measures	Baseline	During	6	12	Method
			Intervention	Months	Months	
BMI	Height	Х				REDCap
	Weight	Х	X (weekly)	Х	Х	REDCap
Medications	Brief Medication Questionnaire ¹⁰	Х		Х	X	REDCap
Blood pressure	Blood Pressure	Х		Х	Х	REDCap
Demographics	Income, employment, marital status, race/ethnicity, household composition*	Х				REDCap
Medical History	Assesses exclusionary medical conditions*	Х				REDCap
Personality factors neuroticism/ openness	Ten-Item Personality Inventory (TIPI) ¹¹	Х				REDCap
Binge Eating Disorder	SCID Interview ¹² for BED	Х				Interview
Physical Activity	Arizona Physical Activity Questionnaire ¹³	Х		Х	X	REDCap
Sleep Quality	STOP ¹⁴	Х		Х	Х	REDCap
	Insomnia Severity Index ¹⁵	X		X	X	REDCap
	Pittsburgh Sleep Quality Index Questions ¹⁶	Х		Х	X	REDCap

	History of sleep apnea diagnosis*	X		X	X	REDCap
	Previous or current treatment for sleep apnea*	X		X	X	REDCap
Depression	BDI ¹⁷	Х		Х	X	REDCap

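### The SAP's primary mixed model tests the condition indicator without a visit-by-condition term or a 12-month contrast, so as written it need not test the 12-month difference to which the 2% margin applies

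*SAP*

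**What the plan says.** The protocol (Data Analysis, Primary non-inferiority outcome) plans one outcome record per person: "We will model percent weight loss at 12 months using a linear regression model framework", with condition as the predictor. There the condition coefficient is the 12-month arm difference.

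The SAP (Primary non-inferiority outcome) changes the model: "We will model percent weight loss at 12 months using a linear mixed model". It then describes the model's terms like this: "with percent weight loss as the dependent variable and study condition as the independent variable and accounting for repeated measures of weight". It keeps the decision sentence that suited the single-record model: "Test of the intervention condition indicator will provide a statistical test of the intervention effect". The target is unchanged, since the comparison is "for percent weight loss at 12 months by our a priori inferiority margin of 2" percent. The section names no visit term, condition-by-visit term, 12-month contrast or covariance structure, and it gives no confidence level.

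On the available weights, the protocol's Study Design says "Follow-up assessments will occur at 6- and 12-months", and its Follow up section says "Participants will complete follow-up visits at 6- and 12-months". The measures table also lists weekly weights during the intervention. The SAP does not say which weights are the repeated measures; the two follow-up visits are the likely ones.

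**The concern.** Once two visits per person are outcomes, a coefficient for condition alone no longer belongs to either visit. It pools the 6- and 12-month arm differences, while the margin and the claim concern month 12 only.

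If Get Social's deficit is smaller at 6 months than at 12, the pooled coefficient flatters it, and non-inferiority can be declared too often when the 12-month deficit is at the margin. If the deficit is larger at 6 months, the trial loses power. If the two are equal, nothing is lost.

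The documents give no arm difference by visit and no ground for assuming equality. Contact tapers in both arms. Traditional groups run "groups will be held weekly for 8 weeks, then biweekly for 16 weeks", that is 8 + 8 = 16 groups, and then monthly, 6 more. The Time Commitment table plans Get Social at 35, then 14, then 8 minutes a week.

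A further cost is that two analysts following the same SAP could test different quantities against the same margin and reach different primary conclusions.

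**Working it through.** **The plan's own figure.** From Protocol, Justification of Sample Size, Aim 1: margin 2, SD 5.5, alpha 0.05, power 90%, true difference 0. Normal approximation: 2 × (1.645 + 1.282)² × 5.5² / 2² = 129.5, so 130 per arm. The noncentral t version gives 131, the stated number, at one-sided 0.05; one-sided 0.025 gives 160. Then 131 / 0.8 = 163.75, so 164 per arm and 328 in total. The sample size reproduces and is not in question. It is a calculation for a 12-month difference.

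**What the condition coefficient estimates.** Let d6 and d12 be the arm differences (Get Social minus Traditional) and V the 2 × 2 covariance of the two outcomes. With condition as the only term that separates the arms, the coefficient is w6·d6 + w12·d12, where w = V⁻¹1 / (1′V⁻¹1).

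- Equal SDs and complete data: w = 0.5 / 0.5 at any correlation.
- A random intercept with common variance, complete data: also 0.5 / 0.5.
- Heterogeneous covariance with SD 5.5 at month 6 and the protocol's alternative 12-month SD of 8.0: w12 = (s6² − ρ·s6·s12) / (s6² + s12² − 2ρ·s6·s12). At ρ = 0.5 this is 8.25 / 50.25 = 0.16. At ρ = 0.7 it is −0.55 / 32.65 = −0.02. These weights apply when a visit main effect is also fitted, or when mean loss common to both arms does not change between visits.

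**Standard errors at 131 per arm, SD 5.5.** The 12-month contrast has SE = 5.5 × √(2/131) = 0.680. The pooled coefficient has SE = 0.680 × √((1 + ρ)/2), which is 0.589 at ρ = 0.5 and 0.654 at ρ = 0.85.

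**Chance of declaring non-inferiority.** P = Φ((w6·d6 + w12·d12 + 2)/SE − z), with z = 1.645 for a 90% CI and 1.96 for a 95% CI. Both are shown because the SAP gives no level. The 6-month differences and ρ = 0.5 to 0.85 are assumptions. Example: d6 = −1, d12 = −2, ρ = 0.5 gives a coefficient of −1.5, and Φ(0.5/0.589 − 1.645) = 21%.

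| True d12 | Assumed d6 | Coefficient | 90% CI | 95% CI |
|---|---|---|---|---|
| −2 | −2 | −2.00 | 5% | 2.5% |
| −2 | −1.5 | −1.75 | 10-11% | about 6% |
| −2 | −1 | −1.50 | 19-21% | 12-13% |
| −2 | −2.5 | −2.25 | about 2% | about 1% |
| 0 | −1 | −0.50 | 74-82% (power) | – |

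For the last row, the 12-month contrast gives Φ(2/0.680 − 1.645) = 90.3%.

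**Does a visit main effect help?** No. In 20,000 simulated complete-data trials per setting with (d6, d12) = (−1, −2) and ρ = 0.5 and 0.8, false non-inferiority with a 90% CI was:
- random intercept: 21.1% and 19.7%
- unstructured covariance with a visit main effect: 21.4% and 20.0%
- 12-month contrast: 4.9% and 5.1%

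**Unequal SDs (5.5 and 8.0), d6 = −1, d12 = −2, ρ = 0.5 to 0.7.** The result depends on the unstated covariance: 16-17% (90% CI) for a common-variance random intercept, 35-44% for a heterogeneous covariance.

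**The case against.** The best defence is that the SAP names 12 months as the target twice. A pooled coefficient contradicts both sentences, whereas a 12-month contrast contradicts neither. Visit terms are omitted, not excluded, and the phrase about repeated measures may be shorthand. That stands: the contrast may well be intended, and under it none of the bias arises. But naming a target does not supply a contrast, and the one coefficient the SAP designates for the test does not estimate that target in general.

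A second objection is that the Traditional taper alone is weak evidence of unequal differences. That is fair. Planned Traditional contact is 16 × 90 = 1,440 minutes and then 6 × 90 = 540. Get Social is 35 × 8 + 14 × 16 = 504 and then 8 × 28 = 224. The ratios are 2.9 and 2.4, so the tapers are similar. They establish neither equality nor a direction.

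A reader might infer that the plan favours Get Social. The documents do not support that: a larger 6-month deficit makes the same test conservative. A reader might also work out a higher error by entering 164 per arm at month 6 and 131 at month 12, which gives 26-28% (90% CI) for a 6-month difference of −1%. That assumes no loss at month 6. The protocol states 20% attrition without timing, so the figure is not one the plan implies.

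Finally, calling the coefficient a weighted average is not always accurate, because the month-12 weight can be about zero or negative.

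**Conclusion.** The concern holds conditionally. If the SAP model is fitted as listed to the 6- and 12-month weights, the tested coefficient is a linear combination of two arm differences and generally equals the 12-month difference only when they agree. The primary test is therefore not uniquely specified. That needs correcting before the primary analysis, whether or not bias would in fact occur.

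The table's error rates, from about 2% to 21% against a nominal 5% (90% CI), and the fall in power from 90% to 74-82% illustrate both directions. They rest on the planned SD of 5.5, 131 complete pairs per arm, and assumed 6-month differences and correlations; they are not forecasts. The documents do not show that the sponsor will use the pooled coefficient, that a false claim is likely, or that weights taken between visits will enter the model. No effect size is claimed for that last point.

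**What to change.** In the SAP's primary outcome section:

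- Specify fixed effects for condition, categorical visit (6 and 12 months) and condition-by-visit.
- Use a covariance that allows different variances by visit, for example unstructured.
- Base the margin test on the condition contrast at 12 months against −2%, and state the confidence level.
- State that only weights measured at the 6- and 12-month study visits enter as outcomes.

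The cost is a few sentences and a few lines of code. N stays at 328. The contrast has a somewhat larger standard error than the pooled coefficient (0.68 against 0.59-0.65 with complete data). If the arm difference truly is constant at 0, power is 90.3% against 92-96% (90% CI). The planned 90% power is kept at 131 per arm and one-sided 0.05; with a two-sided 95% CI it would be 83.7%. At the alternative SD of 8.0 it is 65% (90% CI), the same as for the protocol's 12-month regression, so that limit does not come from the fix. If the contrast was always intended, the change only writes it down.
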